1. INTRODUCTION

Studies of rituximab, a chimeric monoclonal antibody against CD20 have shown that B-cell depletion is of significant clinical benefit as a treatment of relapsing forms of multiple sclerosis (MS).¹ Ocrelizumab is a humanized monoclonal antibody that targets CD20 and selectively depletes CD20 expressing cells, while preserving the capacity for B cell reconstitution. When compared with rituximab, ocrelizumab is associated with increased antibody-dependent cell-mediated cytotoxic effects, and reduced complement-dependent cytotoxic effects in vitro.² By increasing antibody-dependent cell mediated cytotoxic effects, ocrelizumab might modulate tissue-dependent mechanisms of pathogenic response more effectively compared to rituximab. As a humanized molecule, ocrelizumab is expected to be less immunogenic with repeated infusions and might thus present a more favorable safety profile when compared to rituximab.²

Despite rituximab's current off label use in the treatment of MS, currently there is only data available from phase 2 trials and open label trials. The HERMES group conducted a phase 2, double-blind, 48-week trial involving 104 patients with relapsing forms of MS; 69 patients received 1000 mg of intravenous rituximab and 35 patients received placebo on days 1 and 15.³ A significantly higher number of patients in the rituximab group (78.3%) versus the placebo group (40.0%) had an infusion related reaction (IRR) events within 24 hours after the first infusion. Within 24 hours after the second infusion, fewer patients in the rituximab group (20.3%) than in the placebo group (40%) had similar events. A majority of the rituximab group with IRR events (92.6%) were classified as mild to moderate (grade 1 or 2) in severity.

Safety data from the Investigators Brochure on the OPERA I and II phase 3 trials comparing ocrelizumab to interferon β -1a on relapsing MS patients showed that IRRs were the most common adverse events experienced by patients treated with 600 mg of ocrelizumab.⁴ The percentage of patients experiencing IRRs was higher in the ocrelizumab group (relapsing forms of MS: 34.3%; primary progressive forms of MS 39.9%) compared with the interferon β -1a (active control) group who received placebo infusions (relapsing forms of MS: 9.7%; primary progressive forms of MS: 25.5%). The rate of IRRs was highest during the first infusion or Dose 1 (27.5% on Day 1; 4.71% on Day 15 of Dose 1) and decreased over time (13.7%; 9.6% and 7.8% following Dose 2, 3, and 4 respectively) for the ocrelizumab treated group. Comparatively, interferon β -1a users experienced 6.5% of IRRs on Day 1, 2.58% on Day 15, \leq 2.00% after doses 2, 3 and 4 respectively. The reported IRRs were primarily mild-to-moderate in severity (Grades 1 and 2). Serious IRRs occurred in 0.1% and 1.0% respectively of relapsing and progressive patients and treated with ocrelizumab.

Clinical data describing the efficacy and tolerability profile of rituximab and ocrelizumab has utilized populations with different prior treatment characteristics. In the phase 2 HERMES trials, a majority (78.5%) of rituximab patients had been **previously been treated** with a disease modifying therapy in the last 2 years.³ In contrast, the OPERA I and II phase 3 clinical trials, a majority of ocrelizumab

patients (72.9% in OPERA I and 73.8% in OPERA II) represented a **treatment naïve population**.⁴ Examining IRRs in patients who have switched from rituximab to ocrelizumab versus those continuing on rituximab will evaluate the magnitude of the IRRs and subsequent tolerability of ocrelizumab in a real world population of MS patients previously been exposed to rituximab.

Earlier concepts of MS disease pathology have suggested that pathogenic T cells are sufficient for the full expression of MS. However, it is now evident that full autoimmune B cells and humoral immune mechanisms also play key roles.⁵ Ocrelizumab is a humanized monoclonal antibody that targets CD20 and selectively depleted CD-20 expressing B cells. CD20 is a B cell surface molecule that is expressed on pre B cells and mature B cells, but not expressed earlier in the development of B cells or on mature plasma cells. In all three ocrelizumab studies (with relapsing and progressive populations), treatment with 600 mg of ocrelizumab led to rapid and complete depletion of circulating CD19⁺ B cells within 14 days post treatment.⁴ B cell depletion was sustained throughout treatment period. The median time to repletion of B cells was 72 weeks (range 27-175 weeks). We hypothesize that in switching rituximab treated patients to ocrelizumab, the proportion of patients with B cell depletion (CD19⁺ and CD20⁺ ≤ 1%) 6 months after the first and third infusion of ocrelizumab will be the same as the baseline assessment which will be 6 months after the last dose of rituximab and similar to findings in OPERA I and II.

Immunogenicity results from the OPERA I and II trials examined the number of patients who had treatment induced anti-drug antibodies (ADA) to ocrelizumab.⁴ Of the 807 patients who received ocrelizumab and had an ADA assay from a post baseline sample during the controlled treatment period, 3 patients (0.4%) showed treatment induced ADA to ocrelizumab. Of these, 1 patient tested positive for neutralizing antibodies (NAB) to ocrelizumab. During the open label extension phase, the prevalence of ADA continued to remain low with post baseline incidence of 1.9% (2/103 with treatment induced ADA). Currently there is little evidence examining the prevalence of treatment induced ADAs to both rituximab and ocrelizumab in patients that switch from the former to the latter in comparison to continuing rituximab patients. Therefore, we will perform assays to detect ADAs to both rituximab and ocrelizumab in all patients switching from rituximab to ocrelizumab at Day 1, 6 months and between 12 and 18 months on ocrelizumab.

Finally, IRRs have been hypothesized to be a reaction by autoantibodies to the treatment drug or possibly from the release of cytokines from CD20 expressing cells as they are destroyed by ocrelizumab causing a “cytokine storm”. Understanding this process may lead to mechanisms that may aid in ameliorating these infusion reactions. If they are associated with ADA, then it might be possible to predictively premedicate these patients only. Alternatively, if they are associated with cytokine release, it may be possible to eliminate premedication in patients who are already CD20⁺ cell depleted in subsequent infusions. Therefore, we will assay the profile of certain cytokines in the serum 4 hours after start of ocrelizumab infusion.

Since ocrelizumab has entered the market, third party payers within and outside the US have required that the FDA or EMA approved versions of anti-CD20 monoclonal antibodies be used in the treatment of MS, namely ocrelizumab. Currently, we estimate several thousand MS patients in the US and Sweden are taking rituximab currently. Thus, it will be important to demonstrate that switching from a chimeric anti-CD20 to a more fully humanized anti-CD20 does not lead to unexpected infusion reactions and does not increase the probability of development of anti-drug antibodies.

The Rocky Mountain MS Center (RMMSC) at the University of Colorado Anschutz Medical Campus prescribed rituximab infusions for 533 MS patients in the last 12 months, of which 323 patients received their infusion at the University of Colorado Hospital's Outpatient Infusion Center between September, 2015-March, 2016. The RMMSC is one of the few sites nationwide with large numbers of MS patients treated with rituximab. On March 28, 2017, Ocrevus (ocrelizumab) was approved by the FDA for the treatment of primary progressive and relapsing multiple sclerosis. With the approval of ocrelizumab, current rituximab users are being counselled by their MS providers at RMMSC to consider switching to ocrelizumab if it is the only anti-CD20 MAB covered by their insurance.

2. OBJECTIVES

2.1 Primary Objectives

Primary objective: Our primary objective is to assess the frequency and severity of IRRs in MS patients with sustained use rituximab (≥ 2 infusions) at least six months apart who switch to ocrelizumab (**switching group**). IRRs will be compared to: a) patients continuing to receive rituximab (**comparator group**) at each infusion cycle, and b) with rates observed in the OPERA I and II randomized clinical trials after the first and second infusion of ocrelizumab. Grading criteria for IRR will be assessed using the Common Terminology Criteria for Adverse Events (CTCAE) developed by the National Cancer Institutes and utilized in the OPERA I and II trials.⁶ We will also compare the rates of IRRs between the first, second and third dose of ocrelizumab. In addition, patient reported outcomes of their experience with IRRs will also be captured at all infusions of ocrelizumab..

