4.9.4 Safety Analysis

The default analysis will be available case for all eligible participants on an intent to treat basis. Alpha = 0.05 for all tests. As in the OPERA I and II randomized clinical trials, the primary and secondary end points will be descriptively presented. Frequencies and percentages for the severity of IRR grades (Grades 0-5) will be presented for both study groups following each infusion time point and overall between groups. 95% confidence intervals for the proportions will be calculated. Differences in the distribution of IRR severity grades between independent samples (i.e. comparison between groups at a common time point) will be tested with the chi-square or Fisher's exact association test, and additionally with ordinal or multinomial logistic regression. If sample sizes are small among some levels of IRR severity grades, they may be collapsed or dichotomized (i.e. Grade 3 or higher, any reaction or no reaction, severe reaction or none as examples) and methods described for binary outcomes under secondary endpoints will be utilized. Dichotomization may be used to make analysis and presentation of results more manageable as well.

The primary endpoint will be the proportion of whether any IRR occurred (yes or no) per infusion cycle per patient in each study group. The secondary endpoints include the proportion per infusion per patient of severe infusion reaction (grade 3 or greater), the proportion of infusion reactions and severe infusion reaction per patient across all infusions, the proportion patients with anti-drug antibodies, and the proportion of patients with depleted B cells. The primary outcome, binary occurrence of IRR per infusion per patient, could be analyzed with logistic or relative risk models, with GEE (generalized estimating equations) and/or GLMM

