(generalized linear mixed models) methods to incorporate correlation on repeated infusions on a patient. The same method will apply to other longitudinal binary outcomes. Poisson or negative binomial models with exposure terms could calculate rates of IRR per infusion per patient as a counting process. Similar methods will be used to compare IRR rates between the switching group and OPERA I and II phase 3 clinical trials. The total number of IRRs experienced in each patient, will be analyzed with Poisson or negative binomial models. Paired T tests will be used to assess differences in specific cytokine markers between pre and post infusion at each infusion cycle. Patient reported outcomes will also be reported descriptively. Frequencies and proportions will be reported for adverse and serious events and loss to follow up

As contingency methodology, exact tests and confidence intervals for measures of association between categorical variables can be utilized when necessary, if the sample sizes for some of the cells are small. Transforms or rank based methods, such as Wilcoxon sign rank, can be used in place of the T-test if deviation for normality is severe. Otherwise the T-test is a robust test of mean differences for medium to large sample sizes. If matching leads to good balance between the treatment groups on the demographic and disease variables, including age, MS disease duration, and baseline PDDS score, then confounding will not be an issue and the proposed unadjusted tests should be adequate. Alternatively, if the demographic and disease variables are not balanced, then regression or propensity score methods will be used to adjust for potential confounding. Sensitivity analysis comparing unadjusted and adjusted results will be used to determine the extent of the confounding effect. Adjustment for covariates can sometimes improve the precision of the estimated treatment difference by reducing random noise in the outcome.

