4.9.6 Determination of Sample Size

The sample size will be a convenience sample. It is anticipated a minimum of 100 patients will qualify for each cohort (200 total) resulting in studying 300 infusions with ocrelizumab and 200 infusions with rituximab. This is an observational study not designed to demonstrate superiority of ocrelizumab over rituximab in efficacy but instead indicate the magnitude of the relative tolerability and immunogenicity. The primary endpoint is the difference in the percentage of IRRs between the two study groups. In addition, both study groups will include treatment experienced patients on rituximab who have experienced a minimum of two infusions and either continue to stay on rituximab or switch to ocrelizumab.

To estimate study power with the proposed sample size of 100 infusions in each group, we conducted a chart review of 50 patients at the Rocky Mountain MS Center who are currently taking rituximab and examined their IRRs using the proposed IRR grading scale (see section 3.3.1) from Grade 0-5. The number and severity of IRRs were captured following their third rituximab infusion. The highest grade of an IRR that occurred during the infusion was recorded. Our pilot data revealed that following the third rituximab infusion, 14.3% of patients had an IRR of which 85.71% were Grade 0, 12.24% were grade 2 and 2.05% were Grade 3. Hauser et al., found that following the second infusion of rituximab in patients, the majority of whom (60%) were not taking a DMT for 6 months prior to initiating rituximab only 20.3% experienced in an IRR.³

Using IRR estimates from our pilot data and establishing a clinically meaningful difference of 20% increase in IRRs, we conducted the following power analysis for a sample of 95 patients (assuming a 5% attrition rate after recruiting 100 patients in each study group). An IRR proportion for ocrelizumab users at 34.3% compared with 14.3% for rituximab (obtained from our pilot data) for a two sided (alpha = 0.05) two sample proportion test for the null hypothesis of no difference between rituximab and ocrelizumab in proportion of IRRs would result in 90% power for 95 patients per group.

In response to the FDA IND letter, “the power analysis in Section 4.9.6 of the protocol appears to compare the infusion-related reaction (IRR) rate at the third rituximab infusion (14.3%) to that of the first infusion of OCR (34.3%). Because

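### The OPERA comparison in the primary objective (2.1, 4.9.4) is set up for model-based testing with no allowance for between-trial differences, and should be declared descriptive

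*Combined protocol and SAP*

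**What the plan says.** Section 2.1 gives the primary objective two comparisons. Part (a) sets switchers beside patients who continue rituximab. Part (b) sets them beside OPERA, "with rates observed in the OPERA I and II randomized clinical trials after the first and second infusion of ocrelizumab". Section 3.1 repeats that OPERA comparisons will be made for both outcomes.

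Section 4.9.4 first says that logistic or relative risk models with GEE or GLMM could be used for the binary IRR outcome, and Poisson or negative binomial models for rates. It then says: "Similar methods will be used to compare IRR rates between the switching group and OPERA I and II phase 3 clinical trials". The same section sets "Alpha = 0.05 for all tests". It also promises descriptive presentation of the endpoints and 95% confidence intervals for proportions.

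The Introduction gives placebo-infusion figures from two trial programmes. For HERMES, on the first infusion: "A significantly higher number of patients in the rituximab group (78.3%) versus the placebo group (40.0%) had an infusion related reaction (IRR) events"; the placebo figure after the second infusion is 40%. For OPERA, interferon controls who received placebo infusions: "users experienced 6.5% of IRRs on Day 1, 2.58% on Day 15".

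**The concern.** The switchers and the OPERA patients come from different studies. Their IRR rates can differ because of who was enrolled, background treatment, the time window, the setting and how reactions are recorded, as well as because of prior rituximab. A model fitted to the two sources treats everything beyond sampling error as the effect of interest. The plan names no between-study variance, no bridging through a common control and no covariate adjustment for this comparison. The limitation stated in 4.2 concerns only the two study groups, and the matching and propensity methods in 4.2 and 4.9.4 are also written for those groups.

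At stake is how part (b) is reported. A significant difference from OPERA could arise with no effect of switching, and a real effect could be masked by a shift in the opposite direction. Either result would carry the label of the primary objective.

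**Working it through.** **1. The plan's own figure.** Section 4.9.6 assumes "An IRR proportion for ocrelizumab users at 34.3% compared with 14.3% for rituximab", "for a two sided (alpha = 0.05) two sample proportion test", and says this "would result in 90% power for 95 patients per group". The pooled proportion is (0.143 + 0.343)/2 = 0.243.
- SE under the null = √(2 × 0.243 × 0.757/95) = 0.0622.
- SE under the alternative = √((0.143 × 0.857 + 0.343 × 0.657)/95) = 0.0605.
- Power = Φ((0.200 − 1.96 × 0.0622)/0.0605) = Φ(1.29) = 90.1%.

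The figure reproduces. OPERA patients do not enter this test. The documents give no power or error rate for the OPERA comparison.

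**2. Placebo-infusion rates in the Introduction.**
- First infusion: 40.0 − 6.5 = 33.5 points.
- Second infusion: 40 − 2.58 = 37.4 points.
- HERMES first infusion against OPERA's overall control rate in relapsing MS: 40.0 − 9.7 = 30.3 points.
- The HERMES placebo arm had 35 patients, so 40.0% is 14/35, exact 95% CI 24% to 58%.
- The 95% CI for the 33.5-point gap is about 19 to 50 points. The OPERA control denominator is not given; assuming 300 or 807 gives the same interval to the nearest point.

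**3. Effect of a non-drug shift on a nominal 5% test.** Inputs: 100 switchers (3.1, 4.1), and OPERA ocrelizumab rates of 27.5% on Day 1 and 4.71% on Day 15 (Introduction), treated as fixed. The test is the exact two-sided one-sample binomial, chosen here for illustration because the plan fixes no specific test. It rejects at Day 1 for 18 or fewer, or 37 or more, patients with an IRR. It rejects at Day 15 for 0, or 10 or more. The rejection probability is the binomial probability of that region at the shifted rate. The shifts are assumptions.

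| Assumed absolute shift | Day 1 (27.5%) | Day 15 (4.71%) |
|---|---|---|
| none | 4.3% | 2.8% |
| +5 points | 19.7% | 51.0% |
| +10 points | 57.9% | 93.6% |
| −5 points | 17.0% | not possible |
| −10 points | 61.4% | not possible |

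**4. Scale of the shift at Day 15.** A 5- or 10-point rise from 4.71% doubles or triples the rate, so the same shifts were also expressed as odds ratios.
- 27.5% to 32.5%: OR = (0.325/0.675)/(0.275/0.725) = 1.27. This moves 4.71% to 5.9%, with 7% rejection.
- 27.5% to 37.5%: OR = (0.375/0.625)/(0.275/0.725) = 1.58. This moves 4.71% to 7.3%, with 19% rejection.

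**5. Sampling error in the OPERA rate.** The OPERA IRR denominator is also not given. Using 807 (the number with an ADA assay, as a stand-in) in a two-sample test gives 19% and 55% at Day 1 and 54% and 93% at Day 15 for +5 and +10 points. Treating the OPERA rate as fixed does not drive the result.

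**6. Why moderate shifts matter.** The 95% half-width for 100 switchers at 27.5% is 1.96 × √(0.275 × 0.725/100) = 8.8 points. A shift of that order is as large as all the uncertainty the test recognises.

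**The case against.** The strongest defence is that little rests on OPERA. The primary endpoint in 3.3.1 is switching against comparator only, 4.9.6 powers only that contrast, and no decision rule uses OPERA. Section 4.9.4 already promises descriptive presentation with intervals, its models are ones that could be used, and no specific OPERA test is written. All of that stands, and it limits the weight of the point. It does not remove it: the OPERA sentence says similar methods will be used, the alpha statement covers all tests, and nothing says that this comparison is exempt.

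Section 2.1 also says that this study uses the same CTCAE grading as OPERA. That may reduce any recording difference, but it does not fix the window, observer, setting or population.

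Four stronger readings are tempting and are not supported.
- **That the 33.5-point gap measures recording differences, or the shift to expect here.** The Introduction does not say why the rates differ. OPERA controls were on interferon, the windows are worded differently (24 hours against Day 1), and OPERA's own programme shows control rates of 9.7% in relapsing and 25.5% in primary progressive MS. The gap is also HERMES against OPERA, not this centre against OPERA.
- **That error rates of 51% and 94% at Day 15 are established.** They hold for absolute shifts only (step 4).
- **That the models need OPERA patient-level data.** Single-infusion comparisons need only counts and denominators; only repeated-infusion models would need individual records.
- **That 2.1 omits the month 6 infusion.** The Introduction equates first infusion with Dose 1, so second infusion may mean Dose 2. The wording is ambiguous, not shown to be an omission.

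**Conclusion.** The point holds as a matter of analysis choice and wording. Part (b) of the primary objective allows a model-based test at 0.05 that counts sampling error only, and the protocol's own figures show that IRR rates after placebo infusions can differ widely between trials. With 100 switchers and a fixed Day 1 rate of 27.5%, a non-drug shift of 5 points would give about 20% rejection and one of 10 points about 58%. At Day 15 the range runs from 7%/19% to 51%/94%, depending on whether the shift is taken on the odds-ratio or the absolute scale. These figures rest on assumed shifts and an illustrative exact test. The documents do not say what the shift at this centre would be.

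A reader might infer that the primary result of the study is compromised. It is not, on this ground: the primary endpoint and its stated 90% power use only the concurrent rituximab comparator.

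**What to change.** In 2.1 and 4.9.4, state that the comparison with OPERA is descriptive. Tabulate switchers' IRR proportions with exact 95% confidence intervals at Day 1, Day 15 and month 6 beside OPERA's 27.5%, 4.71% and 13.7% (Dose 2). Make no hypothesis test. Add a caveat that differences may reflect population, setting and recording. Naming the three time points also settles what second infusion means.

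Keep the switching-against-comparator test. Keep the planned within-switcher comparison of Day 1 with Day 15 and month 6 (3.3.1), which does not depend on cross-trial rates.

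The cost is a wording change and the loss of a formal test against OPERA. Data collection, sample size and the stated power do not change.

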2.2 Secondary Objectives

Secondary Objective: Our secondary objective is to assess the impact of switching from rituximab to ocrelizumab (**only in the switching group**) on the incidence and prevalence of anti-drug antibodies to ocrelizumab. The presence of anti-drug binding antibodies will be assessed prior to the first and third ocrelizumab infusion and six to twelve months after the last ocrelizumab infusion. The serum drawn before the first infusion of ocrelizumab will be the baseline comparator since these patients will only have been exposed to at least two rituximab infusions over 6 months with no prior exposure to ocrelizumab. This means we will have 100 serum samples prior to ocrelizumab exposure and 200 after ocrelizumab exposure. These assays will be performed by PPD Bio A

Laboratories (in Richmond, VA) who will assess the anti-drug antibodies to ocrelizumab”, and “QPS (Netherlands) who will assess the anti-drug antibodies to rituximab as a single batch once all samples have been collected and cryopreserved.

Other secondary objectives that will be assessed in **the switching group** only include the following:

- a. We will assess the percent of ocrelizumab treated patients that exhibit early recovery of CD19+ and/or CD20+B cells (>1%) prior to each ocrelizumab infusion and at month 12 or 18 which is 12 or 18 months following the first infusion of ocrelizumab. We will compare this to the percent of patients with evidence of early recovery from rituximab as assessed by the baseline B cell panel. Our test will also identify CD19 antigen expression to confirm depletion since presence of anti-CD 20 MAB in patients blood may confound the CD-20 expression assay.
- b. We will assess cytokines to evaluate for possible contribution of a cytokine storm to infusion reactions. Cytokines will be assessed using the MesoScale platform. These blood samples will be collected before the start of each ocrelizumab infusion and following infusion completion. Blood samples will also be collected during a moderate or serious IRR.
- c. We will describe all adverse events and serious adverse events in addition to IRRs (for example infections) as described in the investigator’s brochure.

